Title: Treatment of Acute Pericarditis With Anakinra

NCT #: NCT03224585

Document approval date: June 8, 2017

Document Type: Protocol

TREATMENT OF ACUTE PERICARDITIS WITH ANAKINRA: A PILOT STUDY

Acute pericarditis is a clinical syndrome characterized by an inflammation of the pericardial layers¹⁻². It can be caused by a variety of infectious and non-infectious agents, but it most commonly either follows a viral infection of the upper respiratory tract (when the virus is gone) or has no apparent cause, in which case it is referred to as idiopathic¹⁻². **Acute pericarditis** occurs rather abruptly in previously healthy individual, generally a child or young adult. While the prognosis of acute pericarditis is favorable, with most cases resolving within few days, it is associated with chest pain and discomfort, often severe and requiring an escalation of therapy, and it is occasionally associated with life-threatening complications, such as pericardial tamponade – hypotension and shock due to impaired cardiac filling secondary to large pericardial effusion¹.

Acute pericarditis is diagnosed in 1 in 20 (5%) ED visits for chest pain, 1 in 1,000 (0.1%) hospital admissions, and in 1 in 10,000 (0.01%) healthy individuals¹, reflecting **a significant clinical burden** worldwide.

The **pathophysiology** of acute pericarditis is a stereotypical response to an acute injury to the mesothelial cells constituting the pericardial layers around the heart. The inflammation is initiated by an 'irritant' which can be the virus itself or the release of cellular debris³⁻⁵. The response is however sustained by an amplification of the injury through the activation of the **Nod-like receptor 3 (NLRP3) inflammasome**, an intracellular macromolecular structure responsible for sensing danger or injury and intensifying the inflammatory response through the release of mature Interleukin-1 β (IL-1 β)³⁻⁵. IL-1 β is indeed an apical pro-inflammatory cytokine that stimulates the synthesis of inflammatory mediators such as cyclo-oxygenase-2 (COX-2), prostaglandins and subsequent hyperemia, edema, and hyperesthesia characteristic of the acute pericarditis syndrome (Figure 1)⁶. In most instances, by the time the subject presents with chest pain, the initial insult can no longer be identified, and all that is seen in the inflammatory response.

Anti-inflammatory therapy has been the mainstay of the treatment for acute pericarditis, yet there are no drugs indicated and/or approved by the Food & Drug Administration specifically for the treatment of acute pericarditis, and the treatments conventionally used are associated with rate limiting side effects or high rate of recurrences¹⁻². Non-steroidal anti-inflammatory drugs (NSAIDs) are the most commonly used first line treatment. The anti-inflammatory activity of NSAIDs is related to the inhibition of COX-2 and reduction in prostaglandins synthesis, resulting in local control of pain (Figure 1). NSAIDs (such as indomethacin, diclofenac, ibuprofen) are generally effective in controlling symptoms but these drugs significantly increase risk of gastro-intestinal bleeding, hypertension and renal failure, and are associated with a significant recurrence rate after discontinuation of treatment. **Colchicine** is used as a second line drug, and is also highly effective by inhibiting tubulin aggregation and NLRP3 inflammasome formation. Colchicine however is associated with a 15-20% discontinuation due to diarrhea and other gastrointestinal discomforts⁷. and, although rarely, also with bone marrow suppression (Table 1). **Glucocorticoids** (such as prednisone) are rarely used in acute pericarditis because although very effective in controlling acute pericarditis by inhibiting NF- κ B signaling, these drugs increase risk of gastro-intestinal bleeding, hypertension, and are associated with a higher recurrence rate. In some rare cases, acute pericarditis is secondary to another disease such as bacterial pneumonia, cancer invading the pericardium, tuberculosis, connective tissue diseases – in such cases treatment is aimed at the underlying disease. While anti-inflammatory drugs relieve pain in all types of pericarditis, elimination of the offending agent is essential for healing.

[figure not shown]

Figure 1. Pathophysiology of acute pericarditis: an injury due to an infectious or non-infectious pathogen triggers the formation of the NLRP3 inflammasome initiating a local and systemic inflammatory response.

Treatment	Advantage(s)	Disadvantage(s)
Non-steroidal anti-inflammatory drugs (NSAIDs) [i.e. ibuprofen]	Highly efficacious in relieving pain	Increased blood pressure, sodium/water retention, risk of bleeding
Colchicine	Greater response rate when added to NSAIDs, prevents recurrences when added to NSAIDs	Gastrointestinal intolerance (15-25%); bone marrow suppression (rare)
Glucocorticoids [i.e. prednisone]	Preferred in cases of connective tissue diseases	Impaired glucose control, increased blood pressure, sodium/water retention

There is **a clear need to develop novel therapies for acute pericarditis.**

INNOVATION:

As represented in Figure 1, NLRP3 and IL-1 β occupy a central role of in the pathogenesis of acute pericarditis: activation of the NLRP3 inflammasome leads to release of mature IL-1 β , synthesis of COX-2 and prostaglandins and subsequent hyperemia and pain. Subjects with specific mutations in the *Nlrp3* (also known as *cryopyrin*), rendering it constitutively active, experience spontaneous bouts of systemic inflammation – cryopyrin-associated periodic syndromes [CAPS]⁸⁻⁹- which are exquisitely responsive to IL-1 β blockers. The clinical manifestations of CAPS vary from mild to severe systemic inflammation, with acute pericarditis being one of the more severe clinical presentations¹⁰⁻¹¹. These rare cases of genetically mutated *Nlrp3* highlight the importance of NLRP3 in acute pericarditis. Another relatively uncommon syndrome with familiar transmission is recurrent idiopathic pericarditis – a syndrome of isolated recurrent acute pericarditis on an auto-inflammatory basis, and although the gene(s) involved are unknown, idiopathic pericarditis is also responsive to IL-1 β blockers¹². Most cases of pericarditis are however acquired and, generally, related to recent viral infections. Either the transient infection of the pericardial cells by the virus(es) or the injury related to the infection leads to activation of the NLRP3 inflammasome and the NF-kB and COX2-dependent inflammation, which leads to a full blown acute inflammatory response that is at that point 'sterile' – free of virus(s). The clinical syndrome of pain and discomfort is related to the sterile inflammatory response. The beneficial effects of NSAIDs are mediated through inhibition of COX-2 and reduction in prostaglandin production¹⁻². More recently colchicine has been shown to be effective in acute pericarditis¹³. The renewed interest in colchicine as anti-inflammatory therapy in acute inflammatory disease derives from its use as a treatment of gouty arthritis. This has led to a better understanding of the mechanism of action¹⁴⁻¹⁵. In vitro studies now link it to the NLRP3 inflammasome, colchicine inhibits microtubule formation and interfering with the formation of the macromolecular structure composed of ASC (apoptosis-associated speck-like protein containing a caspase recruiting domain), NLRP3, pro-caspase-1 and pro-IL-1 β , and hence preventing activation of the NLRP3 inflammasome and the release of active IL-1 β ¹⁴⁻¹⁵. While effective in many cases, colchicine is limited by dose-dependent side effects, mainly gastrointestinal⁷. IL-1 β blockers are highly effective in treating acute and chronic pericarditis, including those severe cases that are refractory to NSAIDs and to colchicine^{2,16-25}. There are several drugs approved by the FDA as IL-1 β blockers including anakinra (Kineret®), canakinumab (Ilaris®), and rilonacept (Arcalyst®) but none are approved for acute pericarditis²⁶⁻²⁷.

Developing an IL-1 blocker as preferred treatment for acute pericarditis *without the side effects of the currently available treatments*, would be of great clinical, and commercial, impact.

In conclusion, the current treatment for acute pericarditis is based on NSAIDs and/or colchicine. While it is considered standard of care, this strategy is not based on large clinical trials, and failure of this strategy is known to occur in the following terms: 1) Failure to achieve resolution of symptoms; 2) occurrence of side-effects limiting use; 3) early recurrence of symptoms after discontinuation of treatment. Anakinra (kineret) has been shown to treat and cure refractory and recurrent pericarditis. This study is aimed at determining whether anakinra is also effective as first line treatment in acute pericarditis.

Anakinra is likely to have a more favorable risk profile and be more effective than standard of care for acute pericarditis. The risk of anakinra use are limited to injection site reaction (approximately 10% if treatment is continued for 2 weeks or more, less if treatment is given for less than 1 week), a reduction of symptoms and signs of systemic infection which may lead to a more widespread infection at time of diagnosis (this risk is low, <5% per year with continuous treatment, and is reduced by clinical awareness and monitoring for changes in clinical status). The potential benefit is for a rapid and sustained resolution of acute pericarditis without effects on renal function (i.e. non-steroidal anti-inflammatory drugs), gastrointestinal side effects (i.e. colchicine) and increased risk of bleeding (i.e. non-steroidal anti-inflammatory drugs).

SPECIFIC AIMS:

To determine the **efficacy and tolerability** profile of anakinra in acute pericarditis

- **Step I** – Assessment of **acute pain relief** with anakinra at **6 hours**
(additional treatments allowed only as rescue strategy [>9 pain], NSAIDs discouraged)
- **Step II** – Assessment of **subacute pain relief** with anakinra at **24-hour**
(additional treatments allowed, NSAIDs discouraged)

- **Step III – Comparison of 3-day vs 7-day anakinra treatment** with assessment at 7 and 30 days
Randomized doubled-blinded assignment (additional treatments allowed)

Milestones for Step I [Open label anakinra]:

- Relief of chest pain within 6 hours of treatment
 - Comprehensive pain assessment scale and Visual Analog Pain (0-10) scale
- Effects on ECG (ST elevation score)
- Need for rescue pain treatment (opioids) for severe intractable pain
- Interval change in IL-6 levels from baseline to 6 hours
- Side effects profile

Milestones for Step II [Open label anakinra]:

- Relief of chest pain at 24 hours with Visual Analog Pain (0-10) scale
- Effects on ECG (ST elevation score)
- Use of additional analgesic or NSAIDs
- Side effects profile
- Interval change in IL-6 levels from baseline at 24 hours

Milestones for Step III [Duration of Anakinra treatment]:

- Relief and/or recurrence of chest pain on day 7 and 30
 - Comprehensive pain assessment scale and Visual Analog Pain (0-10) scale
- Changes in pericardial effusion at echocardiography on day 7 and 30 vs day 1
- Side effects profile on day 7 and 30
- Recurrence rate leading to urgent office visit, emergency department visit, hospitalization, or other
- Comprehensive metabolic profile and complete cell count with differential on day 7 and 30
- Interval change in CRP and IL-6 levels from baseline to day 7 and 30

Inclusion criteria:

- Age ≥ 12 years in presence of a parent able to provide consent or age > 18 years
- First or recurrent episode of acute pericarditis, defined as the presence of at least 2 of the following:
 - Chest pain (suggestive of pericarditis and not explained by other condition)
 - Pericardial friction rub on physical exam
 - ST-segment elevation and/or PR depression on ECG
 - New or worsening pericardial effusion
- Pain of moderate-to-severe intensity (pain score ≥ 6 on a scale of 0-10 where 0 is no pain at all and 10 is the worst pain ever experienced) at time on enrollment
- Ability to provide written informed consent if 18 years or older or to provide assent in presence of parental consent if 12-17 years of age

Exclusion criteria:

- Pericarditis due to bacterial or fungal infection
- Pericarditis due to malignancy
- Pericarditis after cardiac surgery
- Tamponade or need for pericardiocentesis for diagnostic/therapeutic purposes
- Pregnancy or breastfeeding
- Hypersensitivity to anakinra, latex or products derived from *Escherichia coli*
- Chronic pain syndromes or chronic use of analgesic drugs

Monitoring for use of pain medications

The use of pain medications will be closely monitored during the study.

- During the first 6 hours (Step I)- the use of additional pain medications will be discouraged unless considered a necessary rescue strategy for pain exceeding 9 in 0-10 pain scale.

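### Does admitting recurrent episodes contradict a study described as testing anakinra as first-line treatment?

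*Protocol*

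**What the plan says.** Only the protocol is at hand. It speaks to this point in five places.

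- **Innovation, closing paragraph.** "Anakinra (kineret) has been shown to treat and cure refractory and recurrent pericarditis". The next sentence gives the purpose: "This study is aimed at determining whether anakinra is also effective as first line treatment in acute pericarditis". Just before these, the paragraph lists three ways in which the NSAID and colchicine strategy fails: symptoms do not resolve, side effects limit use, or symptoms return soon after the drugs are stopped.
- **Opening background section.** NSAIDs "are the most commonly used first line treatment", and colchicine "is used as a second line drug".
- **Specific Aims.** The aim is the efficacy and tolerability "profile of anakinra in acute pericarditis". It mentions neither line of treatment nor episode number.
- **Inclusion and Exclusion criteria.** Eligible patients have a "First or recurrent episode of acute pericarditis, defined as the presence of at least 2 of the following" (four listed features), with pain of at least 6 out of 10. The only exclusion that touches earlier drug use concerns chronic pain or chronic analgesic use. NSAID, colchicine or glucocorticoid treatment already given for the attack is not named.
- **Steps I to III.** The headings for the first two steps, "Milestones for Step I [Open label anakinra" and "Milestones for Step II [Open label anakinra", show that everyone receives open-label anakinra at 6 and 24 hours. NSAIDs are discouraged in both windows. Step III randomizes 3 against 7 days of anakinra. One sample size, 14, serves Steps I and II.

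**The concern.** The word "also" in the purpose sentence sets a new question beside something taken as known, and what is taken as known includes recurrent disease. Read that way, first line means a first episode. Every recurrent patient enrolled would then belong to a group in which the protocol already regards efficacy as established. The criteria set no cap, so in principle all 14 could be recurrences.

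Reading the term as drug order does not close the gap completely. A patient whose NSAID or colchicine has just failed in this attack is not excluded, and for that patient anakinra would not be the first drug.

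At stake is the interpretation: a pooled fall in pain in a mixed group of 14 could be reported as evidence for first-line use.

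**Working it through.** **1. The two readings, set against the text**

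| Reading of first line | Support in the protocol | Does admitting recurrences contradict it? |
|---|---|---|
| First episode | The contrast with recurrent disease in the sentence before | Yes |
| First drug used | The background's use of first and second line for NSAIDs and colchicine; the list of failures of standard drugs just before the sentence; NSAIDs discouraged in Steps I and II | No; an untreated recurrence qualifies |

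The second reading has more support. Placed after a list of failures of standard drugs, refractory and recurrent disease most naturally means disease that has defeated those drugs. The contrast is then between use after failure and use at the outset. Discouraging NSAIDs for 24 hours puts anakinra in the place of the usual first drug. On this reading the only gap is the silence on treatment already given for the attack.

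**2. The protocol's own sample size**

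Inputs from the table under Sample size for Steps I and II: SD 3 with change -3 or -4, and SD 2 with change -2 or -3. The significance level is not stated, so two-sided 5% is assumed, with a one-sample (paired) test of mean change against zero.

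Normal approximation: n = ((1.96 + z_power) × SD / change)², rounded up, with z = 0.8416 for 80% power and 1.2816 for 90%. The squared sums are 7.85 and 10.51.

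- Ratio change/SD = 1: 7.85 and 10.51, so 8 and 11.
- Ratio 4/3: 7.85/1.78 = 4.4 and 10.51/1.78 = 5.9, so 5 and 6.
- Ratio 1.5: 7.85/2.25 = 3.5 and 10.51/2.25 = 4.7, so 4 and 5.

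| SD, change | Protocol (80% / 90%) | Noncentral t | Normal | Power at n = 14 (t) |
|---|---|---|---|---|
| 3, -3 | 10 / 13 | 10 / 13 | 8 / 11 | 93.2% |
| 3, -4 | 7 / 8 | 7 / 9 | 5 / 6 | 99.6% |
| 2, -2 | 8 / 11 | 10 / 13 | 8 / 11 | 93.2% |
| 2, -3 | 4 / 5 | 6 / 7 | 4 / 5 | 99.9% |

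The SD 3 rows follow the t calculation, apart from an 8 where t gives 9 (power at 8 is 89.6%). The SD 2 rows follow the normal approximation. The proposed 14 exceeds every entry under either method. It is sized for change from baseline in all enrolled patients, which is what the Specific Aims ask for.

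**3. What a first-line subset would give**

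The case mix is not stated, so subset sizes are assumptions. Power by noncentral t:

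| Subset n | Change of 1 SD | SD 3, change -4 | SD 2, change -3 |
|---|---|---|---|
| 10 | 80% | 96% | 99% |
| 7 | 60% | 83% | 91% |
| 5 | 40% | 61% | 71% |

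The 95% half-width is t(0.975, n-1) × SD/√n. At SD 3 with 14 patients it is 2.160 × 3/√14 = 1.73 points; with 7 it is 2.447 × 3/√7 = 2.77.

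These figures show that a subset would be imprecise. They do not measure a fault in the plan, because they concern a test of change from zero, and no such test separates the drug's effect from the natural course of the attack.

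**4. Would a change help?**

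Suppose all 14 were untreated first episodes. Steps I and II would still have no comparator, and Step III would still compare two durations of the same drug. The limit on a first-line conclusion would remain.

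**The case for a change.** The strongest case for acting is that the sentence states the study's purpose outright, and that purpose and eligibility are both protocol content. A statistical analysis plan could add a subgroup reading but could not make the two texts agree. On either reading the criteria admit patients outside the stated purpose: recurrent patients on one, patients already treated for the attack on the other. Correcting this takes one sentence.

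Part of this stands. The term is undefined, and the criteria do not ensure that anakinra is the first drug for the attack. But the sentence is rationale, and the operative aim beneath it already matches eligibility. Rewording would tidy the text without altering anything the trial does. Episode type and earlier treatment are baseline items usually handled in the case report form or the analysis plan, so the protocol's silence does not show that they go unrecorded. Pooling is itself an inference from the single sample size, since the protocol does not state the analysis grouping.

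**Conclusion.** No change to the plan is needed. The apparent contradiction depends on the less well-supported reading of one background sentence. On the drug-order reading, admitting recurrent episodes is consistent with the stated purpose, and what remains is a loose term and silence on treatment already given for the attack.

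The effect on the planned analysis is nil: the aim, eligibility and sample size agree, and 14 patients give at least 93% power in all four scenarios of the protocol's table, assuming a two-sided 5% paired test. The effect on interpretation is modest. An analyst would describe the episode types enrolled and report the 6- and 24-hour changes as uncontrolled pilot results in acute pericarditis. The caution needed about first-line efficacy comes chiefly from the lack of a comparator, an understood limit of a study titled a pilot, and it would be the same for any case mix.

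This rests on taking the Specific Aims as the governing statement, and on baseline history being collected outside the text shown.

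### Does Step III's recurrence milestone conflict with the protocol's own definition of a recurrent episode?

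*Protocol*

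**What the plan says.** Several places in the protocol bear on recurrence.

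- **Milestones for Step III**, recurrence by resulting care: "Recurrence rate leading to urgent office visit, emergency department visit, hospitalization, or other". No diagnostic criteria are attached, and the closing *or other* is not explained.
- **Milestones for Step III**, recurrence of pain: "Relief and/or recurrence of chest pain on day 7 and 30", measured on the pain scales.
- **Milestones for Step III**, effusion: "Changes in pericardial effusion at echocardiography on day 7 and 30 vs day 1".
- **Inclusion criteria**: "First or recurrent episode of acute pericarditis, defined as the presence of at least 2 of the following". The four items are chest pain, friction rub, ECG change ("ST-segment elevation and/or PR depression on ECG") and new or worsening effusion.
- **Innovation** (closing summary of current treatment): one of three ways in which standard care is said to fail is "early recurrence of symptoms after discontinuation of treatment".
- **Milestones for Steps I and II**: both list "Effects on ECG (ST elevation score", an item that Step III does not have. Step II also lists "Use of additional analgesic or NSAIDs", and Step III has no such line.
- **Monitoring for use of pain medications**: from day 2 to day 30 pain medication is unrestricted, and subjects record all of it in a diary.

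The proposed sample size is 14. It is derived from pain-score changes at 6 and 24 hours, and no recurrence rate or power is given for Step III.

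**The concern.** The inclusion criteria hold the only explicit definition of a recurrent episode, and it needs two of four signs. The Step III milestones cover only two of those signs, chest pain and effusion. Friction rub is a milestone in no step, and ECG drops out after Step II. The recurrence-rate milestone depends on the care a patient goes on to receive and ends in an undefined category.

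Take a patient whose pain returns, who treats it at home and has nothing else documented. In symptom terms this is a recurrence. By the enrolment definition it meets one of the two signs needed. Under the care-based milestone it counts only if *or other* stretches that far. Because home medication is unrestricted in Step III, the protocol itself makes such a patient likely enough to consider.

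If this were a real conflict, it would touch the only randomised comparison in the study. Two analysts could classify the same patient differently, and a later analysis plan could choose a wording but could not recover an ECG that was never taken.

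**Working it through.** There is no stated figure to reproduce, because the protocol gives no recurrence rate, effect size or power for Step III. The check is mainly a reading of the passages, followed by the arithmetic that seemed to give the concern weight.

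**Step 1. One patient under each wording.** Pain returns, is treated at home, and no second sign is documented.

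| Wording | Role in the protocol | Does the patient count? |
|---|---|---|
| Recurrence of chest pain, day 7 and 30 | Step III milestone | Yes, if pain is present at the assessment |
| Recurrence by resulting care | Step III milestone | Only if *or other* includes home treatment |
| Two of four signs | Eligibility | No (1 of 2), but the rule is not applied to outcomes |
| Recurrence of symptoms | Background on standard care | Not a trial outcome |

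Only the first two rows are outcomes. They measure different things, symptoms at a visit and consequences for care, so a patient may be positive on one and negative on the other without any contradiction. A conflict appears only if the third row is carried over from the enrolment rules, which the text does not do.

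**Step 2. Criterion counts.** With four signs there are C(4,2) = 6 pairs. Pain and effusion together make 1 pair, and the other 5 need ECG or rub. Patterns with two or more signs number 6 + 4 + 1 = 11. Those containing both pain and effusion number 2² = 4, leaving 7.

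Of those 7, four contain no chest pain at all (rub + ECG, rub + effusion, ECG + effusion, all three) and have no bearing on pain treated at home. Among the 7 patterns that do include pain, 4 can be read from pain and effusion and 3 cannot (pain + rub, pain + ECG, pain + rub + ECG). These are abstract patterns. The documents give no frequencies, so no share of patients can be derived.

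**Step 3. Weight of one patient.** Assume that all 14 subjects are randomised 1:1, so 7 per arm (the ratio is not stated). One reclassified patient moves an arm's rate by 1/7 = 14.3 percentage points; at an assumed 5 per arm it would be 1/5 = 20 points. The exact 95% interval for 1/7 runs from 0.4% to 57.9%, and for 2/7 (28.6%) from 3.7% to 71.0%.

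The two-sided Fisher p-value is 0.021 for 5/7 against 0/7 and 0.070 for 4/7 against 0/7. One patient can therefore cross 0.05 in an extreme constructed case. For less extreme splits there is nothing to cross: 3/7 against 1/7 gives p = 0.56, and 4/7 against 1/7 gives p = 0.27.

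**Step 4. Would extra ECGs help?** ECGs at both assessments would number at most 14 × 2 = 28. An ECG on day 7 or day 30 does not document an episode that came and went at home on, say, day 15. The milestone lists name outcomes and are not a schedule of assessments, so the missing ECG line in Step III does not show that none is taken.

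**The case for a change.** The strongest case for a change is that an analysis plan can choose among wordings but cannot create observations. If the rate is meant to follow the two-of-four definition, the Step III list names only two of the four signs. Pain that returns and settles between visits could also escape both recurrence milestones, if the chest-pain item is read as status on the day of assessment. The diary would show medication taken, but the protocol does not say that it records the reason. A sentence on what the rate means would cost almost nothing.

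Part of this stands. The phrase *or other* is undefined, and whether it covers an episode treated at home between visits cannot be settled from the text. The limit on the diary is also real.

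The rest does not. The argument about missing observations depends on the enrolment definition governing the outcome, which nothing in the protocol says. Eligibility and outcome definitions commonly differ, since confirming an index diagnosis and following its course are different jobs. A separate line for medication use in Step III would repeat what the monitoring section already collects. A separate line for return of symptoms largely exists as the chest-pain milestone.

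**Conclusion.** No change to the plan follows. The inclusion definition and the Step III milestones serve different purposes, the two Step III items are complementary, and no rule in the protocol produces a wrong result. The residue is one open category in one of six Step III milestones, in a pilot sized on 6- and 24-hour pain.

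Analysts would fill that gap sensibly: tabulate recurrences by type of resulting care, say what falls under the last category, and show chest pain at day 7 and 30 and diary medication by arm alongside. That is detail an analysis plan normally carries; none is at hand here, so its absence from the protocol is not a fault.

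The shift of 14.3 points per patient rests on an assumed 7 per arm and measures the size of the study, not a defect in the definition. This reading would change only if another document applied the two-of-four criteria to Step III recurrence.

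### The only infection exclusion covers infection as the cause of the pericarditis, so a subject with a separate active infection is eligible as written (low-priority safety point)

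*Protocol*

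**What the plan says.** The Exclusion criteria list seven items. The only one that mentions infection reads "Pericarditis due to bacterial or fungal infection". Another is a drug-safety item unrelated to the cause of the disease: "Hypersensitivity to anakinra, latex or products derived from" *E. coli*.

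The risk statement at the end of the Innovation section names few risks of anakinra. One of them is "a reduction of symptoms and signs of systemic infection which may lead to a more widespread infection at time of diagnosis". It adds that "this risk is low, <5% per year with continuous treatment" and that the risk "is reduced by clinical awareness and monitoring for changes in clinical status".

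The opening background section notes that in rare cases "acute pericarditis is secondary to another disease such as bacterial pneumonia, cancer invading the pericardium, tuberculosis, connective tissue diseases". The Innovation section describes the main target population: "Most cases of pericarditis are however acquired and, generally, related to recent viral infections".

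Exposure is short. Step III of the Specific Aims is a "Comparison of 3-day vs 7-day anakinra treatment", and the proposed sample size is 14 subjects. The Milestones list a side-effect profile in all three steps, a cell count with differential on days 7 and 30, and the change in CRP from baseline to those two days.

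**The concern.** The protocol names masking of infection as a risk of its own study drug, but no entry criterion answers that risk. The single infection criterion concerns aetiology: it removes subjects whose pericarditis is infective. It does not ask whether the subject has some other active infection when the first dose is given.

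This cannot be put down to a list that deals only with causes of pericarditis, because the hypersensitivity item is there purely to protect subjects from the drug. One drug risk has a matching exclusion and the other has none.

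What is at stake is the safety of an individual subject. The clearest case is an infection that is suspected but unconfirmed at enrolment, where the drug could delay its recognition. Eligibility belongs in the protocol, so an analysis plan that is not at hand would not settle the matter.

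**Working it through.** The protocol states no figure for this point, so there is none to reproduce. The check is a reading of the criteria against the kinds of subject who might present.

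**Step 1: does any other exclusion catch a separate infection?** The other six items are malignancy, cardiac surgery, tamponade or pericardiocentesis, pregnancy or breastfeeding, hypersensitivity, and chronic pain or analgesic use. None does.

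**Step 2: do the inclusion criteria catch it?** Chest pain counts only when another condition does not explain it. That is one of four diagnostic items, of which any two suffice. It makes entry less likely for a chest infection that explains the pain. It does nothing about a urinary, skin or dental infection.

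**Step 3: does the background narrow the gap?** Yes, in part. It treats bacterial pneumonia and tuberculosis as diseases to which pericarditis can be secondary, so such a subject would probably be excluded as a case of infective cause.

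**Step 4: apply the criterion as written, and as proposed under the fix, to each type of subject.**

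| Subject | As written | With the fix |
|---|---|---|
| Bacterial or fungal pericarditis | Excluded | Excluded |
| Pericarditis secondary to pneumonia or tuberculosis | Probably excluded | Excluded |
| Idiopathic or post-viral pericarditis, known significant infection elsewhere | Eligible | Excluded |
| Same, infection clinically suspected but unconfirmed | Eligible | Excluded |
| Same, trivial infection elsewhere | Eligible | Eligible |
| Post-viral pericarditis with fever and raised CRP, no other sign of infection | Eligible | Eligible |
| Infection that nobody suspects | Eligible | Eligible |

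The gap consists of the third and fourth rows.

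**Step 5: can the scheduled monitoring stand in for an entry rule?** Side effects are assessed at each step, but after the first dose. The cell count and the post-baseline CRP fall on days 7 and 30. In the 7-day group, day 7 is about the end of dosing. In the 3-day group it is about 7 − 3 = 4 days after the end. No threshold or action is attached to either test.

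**Step 6: does the stated annual risk size the point?** Taking the ceiling of 5% per year as an even daily rate, and assuming that the risk ends with the last treatment day:

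- Daily rate: 0.05 / 365 = 0.000137.
- Per subject over 3 days: 3 × 0.000137 = 0.00041 (0.041%).
- Per subject over 7 days: 7 × 0.000137 = 0.00096 (0.096%).
- Over 14 subjects: from 14 × 0.000411 = 0.0058 expected events (all on 3 days) to 14 × 0.000959 = 0.0134 (all on 7 days).

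These figures concern risk that arises during treatment. They do not describe a subject who is already infected at the first dose, which is the case at issue. In addition, the sentence in the protocol attaches the rate to masked and more widespread infection, so reading it as a rate of new infections would be an interpretation.

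**The case against.** The best case against the point is that the protocol states nothing false. It names the risk, calls it low and names a mitigation, in a pilot of 14 subjects dosed for at most seven days. A clinician would often decline an infected patient without being told to. The masking argument is also weaker for an infection already known, since that diagnosis has been made, and an infection nobody suspects would pass any reworded rule.

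Much of this stands, and it is why the priority is low. It does not remove the point. The criterion is a stated rule, and followed as written it admits the subject in question. Clinical judgement has most need of a rule when an infection is suspected but unconfirmed.

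A reader might go further and infer that the protocol is also at fault for having no rule to stop injections on suspected infection. No such rule is written, but that is missing detail, not a misstated rule. Treating clinicians would ordinarily supply it, and the content of such a rule is debatable: whether suspicion alone suffices, whether dosing may resume, and whether the assignment may be revealed. Mandatory stopping could also shorten exposure in the 7-day group and so blur the comparison of durations.

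A reader might also infer that safety goes unmonitored. The Milestones contradict that.

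**Conclusion.** The point holds as a low-priority safety matter. The one infection exclusion is worded by cause, and a subject with a separate active infection is eligible under it, although the protocol itself warns that the drug can mask infection. The remaining gap is mainly significant bacterial, mycobacterial or fungal infection away from the chest, known or suspected at enrolment.

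Its size is not estimated, because the documents give no prevalence of such infection in patients presenting with pericarditis. Among 14 subjects the number may be zero. The small treatment-period figures in the working should be read neither as a measure of this gap nor as reassurance about it.

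The conclusion rests on two assumptions: that the criteria are applied as written, and that pericarditis accompanying pneumonia or tuberculosis would be classed as infective in cause. If the second fails, the gap is somewhat wider. The documents do not support a claim that the efficacy findings are compromised.

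**What to change.** Extend the first exclusion so that it reads:

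> "Pericarditis due to bacterial or fungal infection", or known or clinically suspected active, clinically significant bacterial, mycobacterial or fungal infection at any site at enrolment; recent viral illness, fever and raised CRP, singly or together, do not by themselves exclude.

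The requirement of clinical significance keeps a trivial skin or dental problem from barring entry. The last clause protects the post-viral population for which the trial is meant, in whom fever and raised CRP may well occur together.

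The cost is one reworded line, with no new test, visit or committee. The downside is that an otherwise eligible subject will occasionally be declined.
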